7.4 Staff assessments

Staff satisfaction and estimated time spent on the ILS Program implementation will be collected by a 5 minute survey during followup. Questions include overall satisfaction with the NH PRIDE study, estimates of total amount of time staff spent on study, satisfaction with key components of the study, reasons for not accepting pharmacologic and nonpharmacologic recommendations, and likelihood that staff would recommend the study to a colleague. The survey will be made available to staff electronically using the Qualtrics Survey Platform and will be administered at the beginning of a regularly scheduled Zoom meeting. After staff have completed the survey, the research team will ask three open ended questions on what worked well and what could have been improved during the study. The meeting will be recorded on the Zoom platform and will be transcribed by study staff. Staff will be informed at the beginning of the meeting that it is being recorded and can choose not to participate.

Surveys related to deprescribing, osteoporosis treatment, and medical provider workflow will be administered to nurse practitioners and physicians via zoom meeting or via the Qualtrix Survey Platform. Zoom meetings will be recorded and transcribed by study staff. Staff will be informed at the beginning of the meeting that it is being recorded and can choose not to participate. Participants will receive a 50.00 gift card.

8. HUMAN SUBJECTS PROTECTION

Because the ILS is providing guideline recommended clinical care to residents, and all resident-level data collection is via the EMR (i.e., no direct resident contact) we request waiver of informed consent and HIPAA authorization for resident data collection.

Because staff are voluntarily participating in the interviews on injury prevention and the videoconferencing component of the program, we request waiver of documentation of informed consent to record their interview and obtain feedback about the ILS.

Because proxies/residents who participate in the interviews are voluntarily participating in the low-risk activity, we request a waiver of documentation of informed consent. Study staff will verbally describe the procedure (in person for residents, over the phone for LARs), and provide written material for review before participating in the interview.

8.1. Sources of Data

Qualitative interviews. Approximately 15 staff and 15 residents/proxies will participate in an audiorecorded interview on falls prevention prior to study implementation. Interviews will be transcribed and we will use qualitative software (NVivo) to analyze themes. Approximately 5 staff and 5 proxies will participate in a follow-up audiorecorded interview to understand implementation barriers.

Resident NH records: We will obtain information on medical diagnoses, medications, behaviors and adverse events from the EMR (see description of data to be obtained in **Section 7**).

MDS records: We will request limited information from the MDS for all participants at baseline and quarterly. This includes functional status, depression, pain, falls and injurious falls, behaviors, or unstable or new medical conditions.

Staff surveys. Approximately 60 staff from the 4 facilities will provide data on acceptability and feasibility through a brief survey during follow-up.

8.2. Protection against Risk

The NH-PRIDE study poses minimal risks; however, below we list possible risks and our proposed strategies to minimize them:

- Loss of privacy and confidentiality of research data. Only PHI necessary to complete study aims will be collected. All data will remain behind either the Duke, NH or the Hebrew Senior Life data firewall, all of which meet HIPAA standards for clinical and research data. Data will be transferred between the NH and HSL database via secure data-sharing software (Accelion). No research data containing PHI will be stored on portable devices. PHI/data for eligible residents will be stored on secure Duke servers accessible only to study staff, and communicated to providers by secure email behind the Duke firewall.
- Loss of confidentiality through videoconferencing sessions. Videoconferencing will include discussions of Protected Health Information in an effort to manage medications and behaviors in nursing home residents at the greatest risk for injurious falls. These

conferences will use secure platforms (e.g., Zoom) and we will only discuss information necessary to make informed medical recommendations.

- Loss of confidentiality with audiorecording patient, proxy and provider interviews: After audiorecording the interviews, investigators will use NVivo software to extract themes and touch points described by participants in an open coding process. Short audio clips illustrating each touch point may be re-organized into an ethnography of the fall prevention experience, with audioclips preserving the family and staff voices, while removing most identifiable information.
- Interference of study procedures with Nursing Home staff duties. We recognize that NH staff have competing clinical demands and study procedures may impact resident care. Using successful procedures from prior studies, we will establish preferred communication times and venues with each facility's staff. We will train study staff to avoid interrupting shift change or medication passes.
- Adverse events due to deprescribing medications increasing fall risk. Although guidelines recommend minimizing the dose or discontinuing medications associated with falls in high-risk patients, they may experience adverse drug withdrawal events related to dose changes. These are class specific and include escalating behaviors, worsening depression or functional decline following psychoactive deprescribing; hypertension or tachycardia, or hyperglycemia for cardiometabolic deprescribing. To minimize this risk, we will: 1) ensure that the medical provider has reviewed and concurs with each change by providing a consult note and having them sign all medication change orders; 2) use slow tapers and geriatric dosing ranges under the guidance of the study geriatricians and geriatric pharmacist; 3) develop rapid communication channels between NH staff and the ILS nurse/study team so that any symptoms can be reported early. These include weekly huddles with nursing staff, a study contact phone number, and regular virtual case based education sessions
- Adverse events related to prescribing osteoporosis medication. Adverse drug reactions related to osteoporosis medications include gastrointestinal distress, esophagitis, injection site reactions (for subcutaneous medications), hypocalcemia/hypercalcemia. Rare events such as osteonecrosis of the jaw or atypical subtrochanteric fractures occur in 1/50,000-100,000 patient years of exposure and are not expected in this small, short term study. To minimize risks we will: 1) instruct NH staff on proper bisphosphonate administration procedures (fasting, sitting upright at least 30 minutes, >8 oz water); 2) ensure study protocols do not recommend oral bisphosphonates to residents with dysphagia or known esophageal stricture; 3) ensure vitamin D sufficiency or adequate loading dose prior to beginning oral bisphosphonates; 4) ensure anabolic agents are not given to patients at risk for hyperparathyroidism or with prior hypercalcemia; 4) discontinue antiresorptive agents after 5 years of treatment.

8.3. Potential Benefits of the Proposed Research to Human Subjects and Others

- **Benefits to providers.** The ILS service will reduce the workload of the clinical staff by centrally coordinating programs and communicating with patients and families. NH staff may additionally benefit from educational activities offered during virtual case based education
- **Benefits to NH Residents and Families.** If the program is effective, patients and families will benefit from improved fall prevention services, with fewer expected to suffer painful and debilitating low-trauma fractures and other fall-related injuries.

8.4. Study Discontinuation

Individual NHs may withdraw from study participation at any time at the discretion of their senior management or corporate supervisors. Providers can opt out of any part of ILS Program participation at any time, and while not being asked to provide informed consent for this research, resident proxies can opt out of reading the fliers at the facility or mailed letter and contacting the research team at any time to request exclusion of their resident from ongoing data collection efforts. Participants may choose to terminate data collection via interviews at any time. If a participant withdraws consent, no additional data will be used, although data previously collected and de-identified may remain in the analyses. There are no anticipated circumstances under which subjects will be withdrawn without their consent.

9. SAFETY MONITORING

The study meets criteria for minimal risk. The ILS Program represents best practices in care coordination and medication review for NH residents. All the resident data will be obtained from their medical record, MDS, and staff interviews, and coded at the time of data entry to protect their confidentiality. Given that the program is based on consensus, peer reviewed guidelines, the risk from the ILS with regards to medication management is minimal.

Overall framework for safety monitoring: The study will employ strategies specific to the 4 types of risk expected; 1) loss of privacy and confidentiality of research data; 2) interference of study procedures with Nursing Home staff duties; 3) Adverse drug withdrawal events due to deprescribing medications increasing fall risk; and 4) Adverse drug reaction related to prescribing osteoporosis medication. In addition, we will monitor for suspected abuse and neglect by NH staff.

All safety events will be reported to the PIs immediately upon recognition by study or NH staff, with additional actions as outlined below. An **independent safety monitoring board** (will be alerted to all Serious Adverse Events (SAEs) potentially related to the study within 24 hours of PI notification. The monitoring board will review all other events during bi-annual safety meetings with the PIs.

The safety monitoring board will be appointed by the NIA and comprised of three individuals not otherwise involved in the study. All of the individuals should have expertise in NH care and at least one individual should be a physician.

Information to be monitored:

- Loss of privacy and confidentiality of research data: The PIs will ask study staff to report any potential breaches of data security procedures, such as inadvertent recording or transfer of PHI outside of the firewall, during monthly study meetings. Staff will be reminded to report such breaches immediately. Any identified will be reported to the IRBs, site data privacy officer, and awarding IC within 24 hours of discovery. Staff will be retrained on data security procedures at least annually.
- Interference of study procedures with Nursing Home staff duties: Study staff will enquire about such interference during the structured staff interviews during the implementation, feasibility, and acceptability testing. All reported instances will be reviewed during regular study team meetings, and remediation plans discussed with the Data Safety Monitoring Board as appropriate.
- Withdrawing medications can lead to worsening symptoms. These can include worsening anxiety, depression, or behavior, insomnia, elevated blood pressure, or gastrointestinal upset, or exacerbation of underlying disease. NH staff will be provided with written and telephonic means of communicating with MD/NP if these symptoms occur. If one of these symptoms is significant enough to warrant an unplanned visit from the MD/NP, it will be considered a study-related Adverse Event. Potentially study-related Adverse Events will be recorded in the study database, reviewed with the study PIs to assess relationship to medication changes, and reviewed with the Safety Board during bi-annual safety meetings.
- Serious Adverse Events include death, hospitalization, life threatening events, and unanticipated problems that pose a risk to subjects or others. All such events that are considered study-related as defined above will be reported to the Safety Board, IRBs, and awarding IC within 24 hours.

- Adverse events related to prescribing osteoporosis medication will be monitored in the same fashion as above. The following will be considered potentially study-related: gastrointestinal distress, esophagitis, injection site reactions (for subcutaneous medications), hypocalcemia/hypercalcemia significant enough to warrant an unplanned visit from the MD/NP.
- Resident reports of or suspected abuse and neglect by NH staff witnessed by study staff: Study staff will be trained to report such events to the PIs immediately. We will follow the process described in Human Subjects to report these to the NH leadership and/or the State Ombudsman. Study staff will follow-up within 1 week and then as needed for resolution of the issue. All such events and their resolution will be reported in writing by the co-PIs and within 24 hours to the Safety Board and the IRBs.
- Non-study related Serious Adverse Events (SAEs) including deaths, hospitalizations, and life threatening events and Unanticipated Problems (UPs) will be identified via MDS review quarterly, and additional information (clinical notes, hospital discharge summaries) will be reviewed in the EMR by study staff. These non-study related SAEs will be reviewed by the Safety Board during bi-annual meetings.

The frequency of monitoring varies with the type of event and is described above. Safety Monitoring Board meetings will be scheduled bi-annually. Given the short duration and small sample size of this pilot study, there are no plans for interim analysis or stopping rules.

If a resident discloses acute symptoms, or reports/displays signs of abuse or neglect to study staff during any of the planned interviews, we will employ a process that has worked successfully in other NH studies. We will work with nursing leadership at each facility at the onset of the interviews to establish a plan that will include completion of a standardized report form to be given to the NH Director of Nursing and Administrator within 24 hours

Individual(s) responsible for trial monitoring and advising the appointing entity include the PIs and Independent Safety Board as described above.

10. STATISTICAL CONSIDERATION

This is a pilot study to test design and test implementation of the ILS Program in four nursing home facilities. We will largely use descriptive statistics to present our results, and to inform the sample size calculation for a future pragmatic RCT. The following statistical considerations will be considered:

- Qualitative Study (Aim 1) - Using NVivo software, investigators will identify themes and touch points described by participants in an open coding process. Short audio clips may be created to illustrate each theme and re-organized into *ethnography of the fall prevention experience*, with audio clips preserving the family and staff voices.⁴² A similar process will occur to analyze the post-implementation interviews from staff and proxies, in order to identify themes surrounding implementation barriers.

In addition, the team will use process *flow mapping* techniques to describe each step, however minor, necessary to 1) program the automatic calculation of injury risk using the FRAiL model, 2) deprescribe psychoactive and cardiometabolic medications associated with falls and injury, 3) prescribe osteoporosis treatment to reduce injury risk in the setting of a fall, and 4) introduce other best practices to prevent injurious falls in the NH.

- ILS Implementation (Aim 2) - Quantitative measures of acceptability, demand, fidelity, and practicality as defined in **Table 1** will be described using descriptive statistics. As is standard in pilot studies, our sample size target is based on the expected proportion of high-risk residents in the 4 pilot facilities and no statistical testing is planned, thus, formal power calculation was not conducted. However, our goal is to achieve 50% adherence with suggested medication changes, and our sample of 80 residents is sufficient to demonstrate this with a 95% Confidence Interval of +/- 5% [95% CI assuming SD 10% is 47.8-52.2%; assuming SD 20% is 45.6-54.5%]. We will refine the ILS Program until >50% acceptance of ILS recommendations is achieved, using the targets set in Table 1.

Following current recommendations, we will not power the future pragmatic trial on the results of this small implementation study with unstable efficacy estimates, but rather we will use our clinical knowledge and results of previously published trials of deprescribing in order to inform the sample size calculation.⁴³

- Validate Injurious Falls (Aim2c) - We will compare the occurrence of falls with injuries using MDS data with the occurrence according to chart review. The MDS defines major injury as any fall resulting in a fracture, joint dislocation or intracranial hemorrhage, whereas a minor injury includes falls resulting in abrasions, lacerations requiring sutures, hematoma, or pain. Participating facilities (Croasdaile Village and Hebrew Rehabilitation Center) will be asked to provide limited MDS data for all residents in the facility. A research assistant will conduct a chart review (all provider and nursing notes from EMR) of a random sample of approximately 300 patients to determine whether any injurious falls were documented. Agreement between the MDS and chart review will be compared using Cohen's Kappa test. We will also calculate the sensitivity, specificity, and positive and negative predictive value of the MDS to identify injurious falls, as compared with the gold standard of chart review.

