2.3. Study Design

This protocol describes refinement and pilot testing activities for the Injury Liaison Service outlined above. The following study designs will be employed:

- 1. Qualitative interviews** will be conducted with approximately 10 NH staff (i.e., nurse, certified nurse aide (CNA), physician, and nurse practitioner who have been employed in a nursing facility for at least 3 months) to gain a better understanding of effective and non-effective injury prevention strategies. Information from these interviews will be used to refine the program during co-design meetings with key stakeholders
- 2. A non-randomized pilot program in four nursing home facilities** will provide data on the implementation of the ILS Program. This includes cross-sectional measures of acceptability, demand, practicality, and feasibility obtained from the electronic medical record (EMR), the IP nurse, and a **post intervention survey** with approximately 60 staff across the four facilities. A **pre-post study design** will be employed in order to measure the safety and efficacy of the ILS Program. Safety and efficacy outcomes will be measured at the resident level.

2.4. Outcome measures. The list of measures, data source, and targets are summarized in Table 1 and described in detail below.

Table 1. Proposed Measures of Implementation, Efficacy, Safety, and Validity with Data Source and Target/Goal

Type	Outcomes	Data Source	Target/Goal
Implementation			
Acceptability	Family acceptance of recommendations	IP Nurse Tracking, staff survey	$\geq 50\%$
	Provider acceptance of recommendations		$\geq 50\%$
	Provider satisfaction		$\geq 80\%$
	Staff participation in virtual case based education program		10 staff/NH/mo.
Demand	Proportion eligible for intervention	IP Nurse Tracking	20%
	Proportion of high risk residents with deprescribing recommendations		50%
	Referral rates to virtual cased based education program		15%
Fidelity	Proportion of targeted staff completing intervention checklists	IP Nurse Tracking	90%
	Cost of IP Nurse per resident		\$225

Practicality	NH staff time	IP Nurse Tracking, staff survey, EMR	<2 hour/mo.	Acceptability: (Primary) Number of families that accepted one or more medication recommendation/ number of families offered a recommendation; Number of patients where
	High-risk Resident 6-mo attrition (death, leave NH)		<40%	
Fidelity/Safety				
Fidelity	No. of deprescribed medications at 3-6 months	EMR	≥1	
	Osteoporosis medication initiation		70%	

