Safety	Behaviors	MDS	<10% increase	
	Functional Decline			
	Unscheduled medical visits	EMR	≤2/facility	
Validation				
Outcome Measure	Injurious falls	MDS and Chart Review	>90% sensitive, >95% specific	

the provider accepted one or more recommendations / number of patients with a medication recommendation; % of staff that indicated they were satisfied or very satisfied with the ILS; proportion of staff that attended one or more virtual case based education sessions

(Secondary) number of total medication recommendations accepted/ total number of medication recommendations; proportion of staff that attended two or more virtual cased based education sessions.

Demand: We will use the FRAiL model to identify residents at greatest risk of injurious falls who are eligible for the ILS Program. Residents with an estimated 2-year risk of hip fracture of ≥5%, or similar target, will be considered high risk and eligible for the program. The facility staff will also be able to refer other at risk patients for participation in the program. Other demand outcomes include the proportion of high risk residents with one or more deprescribing recommendations or with a recommendation for osteoporosis treatment, AND referral rates to virtual case based education sessions, defined as the proportion of high risk residents discussed in these sessions.

Fidelity: At each facility, we will identify targeted staff including nurses and medical providers (physicians, nurse practitioners, or physician assistants) who will be asked to complete the program checklists. Our primary measure of fidelity will be the proportion of staff that complete ≥ 75% of requested checklists. As a secondary fidelity measure we will examine the proportion of resident checklists completed by a provider.

Practicality: We will estimate cost by monitoring the amount of time the IP nurse spends on each eligible resident. Other outcomes include the estimated amount of time the staff spend on the ILS service by self-reported survey AND the six-month attrition of eligible residents from the NH facility due to transfer, discharge to community, or death, as determined by the IP nurse from chart review.

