2.6. Sample Size and Population

We anticipate enrolling approximately 10 NH staff and 10 patient/families for an interview on injury prevention.

We anticipate approximately 20% of long-stay residents at the 4 facilities will be eligible for the medication management program (n=80). See **Section 10, Statistical Considerations** for a full explanation of sample size.

We anticipate conducting interviews to assess the acceptability and practicality of the ILS Program on 60 staff members across the four facilities.

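### Section 10 claims ±5% precision for 50% acceptance with 80 residents; for the yes/no family and provider acceptance measures it is about ±11 points (39–61%)

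*Combined protocol and SAP*

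**What the plan says.** Section 10 (ILS Implementation, Aim 2) states that "our goal is to achieve 50% adherence with suggested medication changes" and that "our sample of 80 residents is sufficient to demonstrate this with a 95% Confidence Interval of +/- 5" percent. The supporting bracket reads "95% CI assuming SD 10% is 47.8-52.2%; assuming SD 20% is 45.6-54.5" percent. The next sentence says the program will be refined until acceptance exceeds 50%, judged against the Table 1 targets. Table 1 sets at least 50% for both family and provider acceptance.

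Section 2.4 defines these two primary measures:

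- Family: "Primary) Number of families that accepted one or more medication recommendation/ number of families offered a recommendation".
- Provider: the number of patients where "the provider accepted one or more recommendations / number of patients with a medication recommendation".

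A secondary measure pools over recommendations: "number of total medication recommendations accepted/ total number of medication recommendations".

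On the origin of the sample, Section 2.6 says "We anticipate approximately 20% of long-stay residents at the 4 facilities will be eligible for the medication management program (n=80"), and Section 10 adds that "no statistical testing is planned, thus, formal power calculation was not conducted".

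**The concern.** The bracketed intervals treat acceptance as a continuous score with an SD of 10 or 20 points. Family and provider acceptance are each a count of yes answers over a count of families or patients. For such an outcome the SD is fixed by the proportion itself and cannot be chosen separately. At the 50% goal it is far larger than either assumed value.

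At stake is how the pilot's acceptance result is read. The sentence is the plan's only quantitative statement of what 80 residents can show about acceptance. A reader who relies on it would take an observed 50% to mean a true rate between about 45% and 55%, and would be too confident that a result just above the target reflects true acceptance above 50%.

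**Working it through.** **Inputs.** From Section 10: n = 80, goal 50%, 95% confidence (taken as two-sided), SD 10 or 20 points. From Section 2.4: yes/no definitions of family and provider acceptance, and the pooled secondary measure. The documents give no ICC, no expected number of recommendations per resident, and no source for the SDs.

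**1. The plan's own figures.** For a continuous mean, the interval is 50 ± c × SD/√80.

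- SD 10: 1.96 × 10/√80 = 2.19, giving 47.8–52.2.
- SD 20: 1.96 × 20/√80 = 4.38, giving 45.6–54.4. With t on 79 df the half-width is 4.45, giving 45.5–54.5.

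Both printed intervals are reproduced to within 0.1 point, so this is the method used.

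**2. The SD of a yes/no outcome.** SD = √(p(1 − p)). At p = 0.50 it is 0.50, or 50 points. Solving in reverse, an SD of 20 points occurs only at p = 4.2% or 95.8%, and an SD of 10 points only at p = 1.0% or 99.0%. Neither is compatible with a 50% goal.

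**3. Precision for family and provider acceptance, n = 80, p = 0.50.**

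- Wald: 1.96 × √(0.25/80) = 10.96 points, 39.0–61.0%.
- Wilson, 40/80: 39.3–60.7%.
- Exact (Clopper–Pearson), 40/80: 38.6–61.4%.

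Relative to the claim: 10.96/5 = 2.2.

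**4. What ±5 would require.**

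- Largest SD that gives ±5 with 80 residents: 5 × √80/1.96 = 22.8 points.
- Independent residents needed for ±5 at 50%: 1.96² × 0.25/0.05² = 384.1, so 385.

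**5. Why ±11 is a best case.** The denominators count only families offered a recommendation, or patients with one. If that were 64 (assumed), the half-width is ±12.2; if 40 (assumed), ±15.5. For clustering, assume 20 residents in each of four facilities and a design effect of 1 + 19 × ICC. These ICCs are illustrations only:

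| Assumed ICC | Design effect | Half-width (points) |
|---|---|---|
| 0.01 | 1.19 | 12.0 |
| 0.05 | 1.95 | 15.3 |
| 0.10 | 2.90 | 18.7 |

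**6. Measures that count recommendations.** Suppose each resident has k independent recommendations, each accepted with probability 0.5. The SD of a resident's percentage accepted is 50/√k, and the half-width over 80 residents is 1.96 × (50/√k)/√80. The pooled secondary proportion has the same half-width when k is equal across residents.

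| k per resident | SD (points) | Half-width (points) |
|---|---|---|
| 2 | 35.4 | 7.7 |
| 3 | 28.9 | 6.3 |
| 4 | 25.0 | 5.5 |
| 5 | 22.4 | 4.9 |
| 6 | 20.4 | 4.5 |
| 25 | 10.0 | 2.2 |

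So ±5 needs about 385 independent recommendations (384.1/80 = 4.8 per resident). With within-resident correlation r, the half-width is 1.96 × √(0.25 × (1 + (k − 1)r)/(80k)). For k = 5 this gives ±5.8 at an assumed r of 0.1 and ±7.3 at 0.3.

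**7. Effect on reading the target.** Suppose true acceptance is 45%. With 80 independent yes/no outcomes (mean 36, SD √(80 × 0.45 × 0.55) = 4.45), the chance of observing more than 50% is about 16%. Under the protocol's SD of 20 points, the standard error is 20/√80 = 2.24, the target lies 5/2.24 = 2.24 standard errors away, and that chance is about 1%.

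**The case against.** The sentence speaks of adherence with suggested medication changes, not of families or patients accepting at least one recommendation. Elsewhere the protocol uses adherence for recommendations taken as a body: Section 2.2 describes an earlier trial that way, and Section 6.2 describes prescriber feedback that way. If the sponsor had in mind each resident's percentage of recommendations followed, a continuous-mean interval is the right method, and the shortfall against ±5 could be small or absent (step 6).

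Part of this stands: ±11 is specific to the yes/no measures. But the documents define no per-resident score, and the next sentence moves to acceptance and the Table 1 targets. The alternative reading does not support the printed figures either. An SD of 20 needs slightly more than six independent recommendations per resident and an SD of 10 needs 25, and the protocol states neither.

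It can also be said that this is a descriptive pilot in which the sentence drives nothing. That is right about the consequence. It limits the weight of the point but does not make the stated precision correct. Strictly, the multiplication in the bracket is sound; the fault is the SD put into it.

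**Conclusion.** The claimed ±5% does not hold for the primary family and provider acceptance measures. With 80 residents and 50% acceptance the 95% interval is about ±11 points (Wilson 39.3–60.7%), 2.2 times as wide as stated. This assumes that all 80 residents contribute to the denominator and respond independently; relaxing either widens it. For the pooled secondary measure, ±5 is attainable only under conditions the protocol does not state.

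The text should be corrected, but the effect is confined to stated precision and interpretation. The 80 rests on expected eligibility, 50% is a point target, and Section 10 says the future trial will not be powered on this pilot's results.

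**What to change.** Delete the intervals based on SD 10% and 20% and replace the precision sentence in Section 10 with, for example:

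> With 80 residents and 50% acceptance, the 95% confidence interval for family acceptance and for provider acceptance is about ±11 percentage points (39–61%). It will be wider if fewer than 80 residents receive a recommendation or if acceptance is correlated within the four facilities.

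The replacement names family and provider acceptance because the other primary acceptability measures are staff-based and do not have 80 residents as their denominator.

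If adherence was meant as a different measure, define it in Section 2.4 and give a source for its SD. If a precision figure is also wanted for the pooled secondary measure, state the expected number of recommendations and the assumed within-resident correlation.

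The cost is protocol wording only: no added residents, data or procedures, and no change to the targets. The stated precision becomes less favourable.
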